6.4 Pharmacokinetics and Product Metabolism

Following oral administration of ibrutinib at doses ranging of 420, 560, and 840 mg/day, exposure to ibrutinib increased as doses increased with substantial intersubject variability. The mean half life $(t_{1/2})$ of ibrutinib across 3 clinical studies ranged from 4 to 6 hours, with a median time to maximum plasma concentration (T_{max}) of 1 to 2 hours. Taking into account the approximate doubling in mean systemic exposure when dosed with food and the favorable safety profile, ibrutinib can be dosed with or without food. Ibrutinib is extensively metabolized primarily by CYP 3A4-mediated metabolic pathways. The on-target effects of metabolite PCI-45227 are not considered clinically relevant. Steady-state exposure of ibrutinib and PCI-45227 was less than 2-fold of first dose exposure. About 8% of ibrutinib is excreted renally. Ibrutinib exposure is not altered in patients with creatinine clearance (CrCl) >30 mL/min. Patients with severe renal impairment or patients on dialysis have not been studied. Following single dose administration, the AUC of ibrutinib increased 2.7-, 8.2and 9.8-fold in subjects with mild (Child-Pugh class A), moderate (Child-Pugh class B), and severe (Child-Pugh class C) hepatic impairment compared to subjects with normal liver function. A higher proportion of Grade 3 or higher adverse reactions were reported in patients with B-cell malignancies (CLL, MCL and WM) with mild hepatic impairment based on NCI organ dysfunction working group (NCI-ODWG) criteria for hepatic dysfunction compared to patients with normal hepatic function.

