7.0 DOSE DELAYS AND MODIFICATIONS

Section 7.1-7.3 outline recommendations for management of ibrutinib-associated toxicity. However, dose adjustments outside these guidelines can be made by the investigator if considered to be in the patient's best interests.

7.1 Recommended dose modifications:

Recommended dose modifications of ibrutinib are described below. For adverse reactions listed in Table 1, interrupt ibrutinib. Once the adverse reaction has improved to Grade 1 or baseline (recovery), follow the recommended dosage modifications.

Adverse Reaction	Occurrence	Dose Modification After Recovery Starting Dose = 420 mg
	First	Restart at 280 mg daily ^c
Grade 2 cardiac failure	Second	Restart at 140 mg daily ^c
	Third	Discontinue IMBRUVICA
Cuada 2 andia androthusia	First	Restart at 280 mg daily ^c
Grade 3 cardiac arrhythmias	Second	Discontinue IMBRUVICA
Grade 3 or 4 cardiac failure Grade 4 cardiac arrhythmias	First	Discontinue IMBRUVICA
Other Grade 3 or 4 non- hematological toxicities ^d	First	Restart at 280 mg daily
Grade 3 or 4 neutropenia with infection or fever	Second	Restart at 140 mg daily
Grade 4 hematological toxicities	Third	Discontinue IMBRUVICA

See Warnings and Precautions.

7.2 Hematologic toxicity:

Interrupt ibrutinib for any Grade 3 or greater neutropenia with infection or fever, or Grade 4 hematological toxicities. Once the toxicity has resolved to Grade ≤1 or baseline, reinitiate ibrutinib as per the table above.

7.3 Non-hematologic toxicity:

Interrupt treatment for any grade 3 or greater non-hematological toxicity. Once the toxicity has resolved to grade ≤1 or baseline, restart the study drugs as per the guidelines for the hematologic toxicity as above.

If the dose of ibrutinib is reduced, at the investigator's discretion, the dose of ibrutinib may be re-escalated after 2 cycles of a dose reduction in the absence of a recurrence of the toxicity that led to the reduction. Dose changes will be recorded in the medical record.

^b Grading based on National Cancer Institute-Common Terminology Criteria for Adverse Events (NCI-CTCAE) criteria, or International Workshop on Chronic Lymphocytic Leukemia (iwCLL) criteria for hematologic toxicities in CLL/SLL.

^c Evaluate the benefit-risk before resuming treatment.

^d For Grade 4 non-hematologic toxicities, evaluate the benefit-risk before resuming treatment.

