7.5 Dose Modification for Hepatic Impaired Subjects

Subjects who develop acute hepatic toxicity with liver enzymes Grade 3 or higher while on study should be managed per standard dose modification guidelines in Section Error! Reference source not found. Ibrutinib is metabolized in the liver. In the population PK analysis (1,202 subjects), 179 subjects (14.9%) had mild hepatic impairment according to National Cancer Institute criteria and 12 subjects (1.0%) had moderate hepatic impairment. These subjects did not show a significantly higher ibrutinib exposure compared with subjects with normal hepatic function. In a hepatic impairment study, data showed an increase in ibrutinib exposure. For subjects with mild liver impairment (Child-Pugh class A), the recommended dose is 280mg daily. For subjects with moderate liver impairment (Child-Pugh class B), the recommended dose is 140mg daily. Monitor subjects for signs of ibrutinib toxicity and follow dose modification guidance as needed. It is not recommended to administer ibrutinib to subjects with severe hepatic impairment Subjects with clinically significant chronic hepatic impairment at the time of Screening (Child- Pugh class C) are excluded from study participation. Concomitant use of strong CYP inhibitors is not permitted in subjects with chronic hepatic impairment. Refer to Appendix D for Child-Pugh classification. Please refer to Table 3 for dose modifications due to hepatic impairment.

Table 1. Dose Modification Guidance for Hepatic Impaired Subjects

Child Pugh	class A	Child Pugh Cla	Child Pugh			
(Mild hepat	ic	(Moderate hepa	class C			
impairment)*	impairment)**	(Severe hepatic			
			impairment)			
Ongoing at	Develops	Ongoing at	Develops	Develops during		
time of	during	time of	during study	study		
enrollment	study	enrollment				

Ibrutinib	280 mg	280mg	140 mg	140 mg	Hold until
Dose					improves to
(daily)					moderate [Class
					B] or better)

^{*} If further reduction is needed due to non-hepatic toxicity, dose may be reduced to 140 mg. In the event that additional reduction is needed, ibrutinib should be held for non-hepatic toxicity until resolution.

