8.2. Medications to be Used with Caution

8.2.1 CYP3A- Inhibitors/Inducers

Ibrutinib is metabolized primarily by CYP3A. Concomitant use of ibrutinib and drugs that strongly or moderately inhibit CYP3A can increase ibrutinib exposure, and strong CYP3A inhibitors should be avoided.

Strong CYP3A inhibitors

Co-administration of ketoconazole, a strong CYP3A inhibitor, in 18 healthy subjects, increased exposure (Cmax and AUClast) of ibrutinib by 29- and 24-fold, respectively. In a dedicated drug-drug interaction study in subjects with B-cell malignancies, co-administration of voriconazole increased Cmax and AUC by 6.7-fold and 5.7-fold,

^{**} If further reduction is needed due to non-hepatic toxicity, ibrutinib should be held until resolution.

respectively. In clinical studies, the maximal observed ibrutinib exposure (AUC) was ≤2-fold in 37 subjects treated with mild and/or moderate CYP3A inhibitors when compared with the ibrutinib exposure in 76 subjects not treated concomitantly with CYP3A inhibitors. Clinical safety data in 66 subjects treated with moderate (n=47) or strong CYP3A inhibitors (n=19) did not reveal meaningful increases in toxicities. Voriconazole and posaconazole can be used concomitantly with ibrutinib. All other strong inhibitors of CYP3A (e.g., ketoconazole, indinavir, nelfinavir, ritonavir, saquinavir, clarithromycin, telithromycin, itraconazole, nefazodone, and cobicistat) should be avoided, and an alternative with less CYP3A inhibitory potential should be considered. If the benefit outweighs the risk and a strong CYP3A inhibitor must be used, please discuss recommendations for dosing with the PI and document the discussion in the medical record.

Moderate and mild CYP3A inhibitors

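### Sections 7.1–7.3 and 7.5 give different instructions for the same non-hepatic toxicity in a patient who starts at 420 mg and develops Child-Pugh A or B impairment on study, and no text says which governs

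*Combined protocol and SAP*

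**What the plan says.** The dose column of the Section 7.1 table is headed "Dose Modification After Recovery Starting Dose = 420 mg". Three kinds of event share its general entries: other Grade 3–4 non-hematologic toxicity, Grade 3–4 neutropenia with infection or fever, and Grade 4 hematologic toxicity. The first occurrence reads "Restart at 280 mg daily", the second goes to 140 mg, and the third reads "Discontinue IMBRUVICA". The cardiac entries also end in discontinuation, at the first, second or third occurrence depending on the event.

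Section 7.2 sends hematologic events to that table: "Once the toxicity has resolved to Grade ≤1 or baseline, reinitiate ibrutinib as per the table above". Section 7.3 begins "Interrupt treatment for any grade 3 or greater non-hematological toxicity" and then refers back to the same steps. Neither exempts a patient with hepatic impairment.

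Section 7.5 has its own table: 280 mg daily for Child-Pugh A and 140 mg daily for class B, with separate columns for impairment present at enrollment and impairment arising on study. Its footnotes deal with non-hepatic toxicity. For class A (footnote *), the dose may go to 140 mg, and then: "In the event that additional reduction is needed, ibrutinib should be held for non-hepatic toxicity until resolution". For class B (footnote **, which appears among the text of 8.2.1), the only step is: "If further reduction is needed due to non-hepatic toxicity, ibrutinib should be held until resolution".

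Two other places bear on this. Section 7.0 lets the investigator depart from 7.1–7.3 in the patient's interest. Section 13 lists removal criteria for all patients: a Grade 4 non-hematologic event at least possibly related to ibrutinib (with a risk:benefit assessment for laboratory-defined events), and an adverse event that makes discontinuation necessary under the protocol's safety criteria or desirable in the opinion of the investigator or subject.

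**The concern.** A patient who starts at 420 mg and becomes hepatically impaired on study meets the heading of the 7.1 table and also sits in a column of the 7.5 table. Both can be read to apply to the next non-hepatic toxicity, and they do not give the same instruction.

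The stakes are mainly safety and consistent conduct. Two physicians could follow the protocol faithfully and treat the same event differently, and one literal reading raises the dose after a serious toxicity. Section 6.4 gives a reason to be clear in this group: "A higher proportion of Grade 3 or higher adverse reactions were reported in patients with B-cell malignancies (CLL, MCL and WM) with mild hepatic impairment". There is also a small reporting consequence. Section 2.0 anticipates that about 10–15% of patients will stop for toxicity; for the affected patients, whether they count as stopped depends on which rule was followed.

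**Working it through.** The plan states no figure for this point, so the check sets the rules side by side. It assumes that the three general event types in the 7.1 table share one set of first, second and third steps, which is how the table reads.

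Take a patient who started at 420 mg, was moved to the 7.5 dose for impairment that developed on study, and now has a first Grade 3 neutropenia with fever. The earlier change was for hepatic impairment, so this is a first occurrence under 7.1.

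| Step | 7.1 via 7.2/7.3 | 7.5, class A (on 280 mg) | 7.5, class B (on 140 mg) |
|---|---|---|---|
| First event | interrupt, restart at 280 mg | may reduce to 140 mg | hold until resolved; no dose given afterwards |
| Second event | restart at 140 mg | hold until resolved; no dose given afterwards | same hold |
| Third event | discontinue | same hold | same hold |

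Change from the current dose if the first step of 7.1 is applied literally:

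- Class A: 280 − 280 = 0 mg, so no reduction, where footnote * allows one.
- Class B: 280 − 140 = +140 mg, twice the current dose. This also contradicts the 140 mg entry for class B in the 7.5 table itself.

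At the last step, every 7.1 row discontinues. Neither 7.5 footnote gives a restart dose after the hold, a limit on repeated holds, or a discontinuation step.

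The pointers in 7.5 do not resolve this. It tells staff to follow dose modification guidance without naming a section. Its reference for acute Grade 3 or higher liver-enzyme toxicity is a failed cross-reference field. It cites Table 3 for a table captioned Table 1, the number that 7.1 uses for its own table.

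Size: the only frequencies are in 7.5, from a population pharmacokinetic analysis in other subjects using National Cancer Institute criteria, not Child-Pugh.

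- Mild impairment: 179/1,202 = 14.9%. Applied to 50 patients: 0.149 × 50 = 7.45, about 7.
- Moderate impairment: 12/1,202 = 1.0%. Applied to 50 patients: 0.010 × 50 = 0.5.

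These show scale only. They describe how common impairment was in that analysis, not how often it arises on treatment, and a qualifying toxicity must also occur. Exclusion 20 in Section 4.2 keeps out active, clinically significant class B or C at entry. A class A patient at enrollment begins at 280 mg, outside the 420 mg heading.

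**The case against.** The best defence is that the 7.1 table limits itself to a 420 mg start, so 7.5 is the specific rule for everyone else. That stands in good part for class A patients enrolled at 280 mg. It does not help a patient who did start at 420 mg and became impaired later.

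A second defence is that the footnotes apply only when further reduction is needed, so they could govern reductions while 7.1 keeps its discontinuation rows, including the one for a first Grade 3 or 4 cardiac failure. This is coherent, and it means the last step can be read as silence in 7.5 and not as contradiction. But no sentence says so, and it leaves the first-step difference untouched.

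Third, a reader might infer that hepatically impaired patients have no stopping point. The documents do not support that. Section 13 applies to everyone, and 5.2 ends study treatment at progression, at confirmed MRD-negative remission or at 2 years. Section 13 is still not a full substitute. Its specific criterion is limited to Grade 4 non-hematologic events, so it misses a first Grade 3 cardiac failure, a third Grade 3 non-hematologic toxicity and a third febrile neutropenia, all of which 7.1 stops. Its general criterion rests on opinion or on the safety criteria that are in question.

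Fourth, a reader might infer that the protocol compels a doubled dose in class B. It does not: 7.1–7.3 are recommendations and 7.0 allows departures. Discretion does not identify the default, however, and the clause does not mention 7.5.

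Finally, a reader might turn the single-dose AUC ratios in 6.4 (2.7-fold in class A, 8.2-fold in class B) into exposure multiples at each dose. The documents do not support firm figures. The population analysis in 7.5 found no significantly higher exposure in mild or moderate impairment, by a different classification, so the point does not rest on such multiples.

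**Conclusion.** The point holds for patients who start at 420 mg and develop Child-Pugh A or B impairment on study. For them, 7.1–7.3 and 7.5 can both be read to apply, they differ at the first step, and 7.5 does not say what follows a hold or whether 7.1's discontinuation rows still bind. It does not extend to a claim that every patient on a 7.5 dose receives incompatible instructions, because the 420 mg heading arguably leaves out those enrolled at 280 mg.

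Few patients are likely to be affected. Borrowing the population analysis gives at most about 7 mild and fewer than 1 moderate case in 50, before asking whether the impairment arose on study and a qualifying toxicity followed. The number could well be zero. The conclusion does not depend on that count: it rests on the wording of the two sections and on the absence of any rule of precedence. It should be corrected because it concerns safety instructions and is cheap to correct. It does not affect the sample size or the primary test.

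**What to change.** Reconcile 7.1–7.3, the 7.5 table and footnotes, and Section 13. The text should state:

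- which set governs non-hepatic toxicity in a patient already on a 7.5 dose, separately for impairment present at enrollment and arising on study if the answers differ;
- what happens once a toxicity held under the 7.5 footnotes has resolved, and whether repeated holds are limited;
- whether the discontinuation rows of 7.1 apply to these patients, and how they relate to Section 13.

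Repair the failed section reference, name the guidance that 7.5 tells staff to follow, and give the hepatic table a unique number that matches its citation. The doses and stopping rules are the sponsor's decision; the request is only that the passages agree.

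The cost is a precedence sentence or a few table rows in a protocol amendment. No change to the statistical design is needed.

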8.0 CONCOMITANT THERAPY

8.1 Allowed concomitant therapy

All concomitant medications will be noted in the patient's medical record. Patients should receive full supportive care during study participation, including hematopoietic growth factors, transfusion of blood products, fluid and electrolyte replacement, anti-emetics, anti-diarrheals, medications to control tumor lysis syndrome and hypersensitivity reactions, and antibiotics when appropriate. Anti-infective prophylaxis for viral, fungal, bacterial or *Pneumocystis* infections is permitted.

Short courses (<=14days) of steroid treatment for non-cancer related medical reasons (e.g. joint inflammation, asthma exacerbation, rash, antiemetic use and infusion reactions) at doses that do not exceed 100mg per day of prednisone or equivalent are permitted.

8.2. Medications to be Used with Caution

8.2.1 CYP3A- Inhibitors/Inducers

Ibrutinib is metabolized primarily by CYP3A. Concomitant use of ibrutinib and drugs that strongly or moderately inhibit CYP3A can increase ibrutinib exposure, and strong CYP3A inhibitors should be avoided.

Strong CYP3A inhibitors

Co-administration of ketoconazole, a strong CYP3A inhibitor, in 18 healthy subjects, increased exposure (Cmax and AUClast) of ibrutinib by 29- and 24-fold, respectively. In a dedicated drug-drug interaction study in subjects with B-cell malignancies, co-administration of voriconazole increased Cmax and AUC by 6.7-fold and 5.7-fold,

^{**} If further reduction is needed due to non-hepatic toxicity, ibrutinib should be held until resolution.

respectively. In clinical studies, the maximal observed ibrutinib exposure (AUC) was ≤2-fold in 37 subjects treated with mild and/or moderate CYP3A inhibitors when compared with the ibrutinib exposure in 76 subjects not treated concomitantly with CYP3A inhibitors. Clinical safety data in 66 subjects treated with moderate (n=47) or strong CYP3A inhibitors (n=19) did not reveal meaningful increases in toxicities. Voriconazole and posaconazole can be used concomitantly with ibrutinib. All other strong inhibitors of CYP3A (e.g., ketoconazole, indinavir, nelfinavir, ritonavir, saquinavir, clarithromycin, telithromycin, itraconazole, nefazodone, and cobicistat) should be avoided, and an alternative with less CYP3A inhibitory potential should be considered. If the benefit outweighs the risk and a strong CYP3A inhibitor must be used, please discuss recommendations for dosing with the PI and document the discussion in the medical record.

Moderate and mild CYP3A inhibitors

In subjects with B-cell malignancies, co-administration of the CYP3A inhibitor erythromycin increased Cmax and AUC by 3.4-fold and 3.0-fold, respectively. If a moderate CYP3A inhibitor (e.g., fluconazole, erythromycin, amprenavir, aprepitant, atazanavir, ciprofloxacin, crizotinib, diltiazem, fosamprenavir, imatinib, verapamil, amiodarone, dronedarone) is indicated, reduce the ibrutinib dose to 280 mg once daily for the duration of the inhibitor use or as per recommended dose modifications described in the specific clinical study protocol. In subjects with cGVHD, if a co-administration of voriconazole and posaconazole (at doses less than or equal to suspension 200 mg twice daily) is indicated, reduce the ibrutinib dose to 280 mg once daily. If a co-administration of higher doses of posaconazole (i.e., suspension 200 mg three times daily or 400 mg twice daily; IV injection 300 mg once daily; delayed-release tablets 300 mg once daily) is indicated, reduce the ibrutinib dose to 140 mg once daily. No ibrutinib dose modifications for moderate inhibitors are required for cGVHD subjects. Follow the specific instructions described in the clinical study protocol. No dose adjustment is required in combination with mild inhibitors. Monitor subjects closely for toxicity and follow dose modification guidance as needed. Avoid grapefruit and Seville oranges during ibrutinib treatment as these contain moderate inhibitors of CYP3A.

Strong CYP3A inducers.

Administration of ibrutinib with strong inducers of CYP3A decreases ibrutinib plasma concentrations by up to 90%.

Avoid concomitant use of strong CYP3A inducers (e.g. carbamazepine, rifampin, phenytoin and St. John's Wort). Consider alternative agents with less CYP3A induction.

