- 9. Free of prior malignancies for 3 years with exception of patients diagnosed with basal cell or non-metastatic squamous cell carcinoma of the skin, or carcinoma "in situ" of the cervix or breast, who are eligible even if they are currently treated or were treated and/or diagnosed in the past 3 years prior to study enrolment.
- 10. A negative urine pregnancy test (within 7 days of enrollment date) is required for women with childbearing potential. Women of childbearing potential include any female who has experienced menarche and who has not undergone successful surgical sterilization (hysterectomy, bilateral tubal ligation, or bilateral oophorectomy) or is not postmenopausal (≥1 year of no menses, by history).

4.2 Exclusion criteria.

- Receipt of any prior therapy for CLL. Patients who have received "early intervention" with INVAC-1 vaccine against hTERT will be eligible provided all the following exist:
 - i) They had no response to the vaccine treatment (persistent CLL >1% in bone marrow).
 - ii) ≥3 months have elapsed since the last dose of vaccine.
 - iii) No residual toxicities attributable to the vaccine exist at the time of study enrollment.
 - iv) The patient does not meet IWCLL criteria for requiring treatment.
- 2. Richter transformation.
- 3. Active malignancy requiring systemic therapy, other than CLL, with the exception of: adequately treated in situ carcinoma of the cervix uteri; adequately treated basal cell carcinoma or localized squamous cell carcinoma of the skin; previous malignancy confined and surgically resected (or treated with other modalities) with curative intent.
- 4. Systemic anticoagulation with warfarin or other Vitamin K antagonists.
- 5. Active and uncontrolled autoimmune hemolytic anemia (AIHA) or autoimmune thrombocytopenia (ITP) requiring daily prednisone dose of >20 mg.
- 6. Current and concurrent use of strong CYP3A4 inhibitors or activators.
- 7. Pregnant or breast-feeding females.

- 8. Uncontrolled and active systemic fungal, bacterial, viral, or other infection (defined as exhibiting ongoing signs/symptoms related to the infection and without improvement, despite appropriate antibiotics or other treatment).
- Any other severe concurrent disease, or history of serious organ dysfunction or disease involving the heart, kidney, liver or other organ system that, in the investigator's opinion, may place the patient at undue risk to undergo therapy with ibrutinib.

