5.0 TREATMENT PLAN

5.1 Recommended prophylactic medications:

The following are recommended prophylactic medications. For individuals who are allergic, an equivalent replacement may be identified:

- Allopurinol 300 mg PO daily for the first 7 days of course 1 is recommended for tumor lysis prophylaxis.
- Valacyclovir 500 mg PO daily for all treatment courses and for at least 3 months after completion of treatment is recommended, for herpes virus prophylaxis.

5.2 Treatment regimen.

Ibrutinib monotherapy will be administered at 420mg once daily until either:

- 1. Disease progression or
- 2. Achievement of complete remission with negative MRD, on two separate assessments, at least 6 months apart. For the purposes of determining treatment cessation, MRD analysis must be performed on bone marrow, using standardized 4-color flow cytometry and demonstrate sensitivity of at least 0.01%.(28) We anticipate a low rate of MRD-negative CR/CRi, which may require prolonged treatment to achieve. Patients who discontinue ibrutinib due to achievement of MRD-negative CR/CRi, will continue to have routine clinical follow-up every 3 months, which will include MRD analysis in peripheral blood, performed at least once per year.
- 3. Completion of 2 years of therapy.

5.3 Long term follow-up.

Patients who remain on therapy at 2 years (the timing of the primary endpoint) may continue ibrutinib, at the discretion of their physician. This would, however, require transition to commercial supply of ibrutinib and should be discussed with the PI. If patients choose to have follow-up at M.D. Anderson, they will be seen every 3-6 months, at the discretion of their physician. If they are receiving follow-up at an outside center, they will be telephoned by study staff every 6 months (until disease progression, death or receipt of a new therapy) to determine:

- Whether they are still receiving study drug.
- Whether any significant toxicity has occurred.
- Whether their disease remains in remission.
- Whether they have had any other cancer therapy.

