6.0 BACKGROUND DRUG INFORMATION

Ibrutinib

Ibrutinib is a small-molecule inhibitor of BTK. Ibrutinib forms a covalent bond with a cysteine residue in the BTK active site, leading to inhibition of BTK enzymatic activity. Ibrutinib 420 mg will be administered orally once daily. Ibrutinib should be administered at the same time each day with 8 ounces (approximately 240 mL) of water. The capsules should be swallowed intact and patients should not attempt to open capsules or dissolve them in water. If a dose of ibrutinib is not taken at the scheduled time, it can be taken as soon as possible on the same day with a return to the normal schedule the following day. Extra capsules of ibrutinib should not be taken to make up for the missed dose.

The first dose will be delivered in the clinic on Day 1, after which subsequent dosing is typically on an outpatient basis. Ibrutinib will be dispensed to subjects in bottles at each visit. Unused ibrutinib dispensed during previous visits must be returned to the site and drug accountability records updated at each visit. Returned capsules must not be redispensed to anyone.

Concomitant use of strong CYP3A inhibitors which would be taken chronically (e.g. ritonavir, indinavir, nelfinavir, saquinavir, boceprevir, telaprevir, nefazodone) is prohibited. Concomitant use of strong CYP3A inducers (e.g. rifampin, rifabutin, phenytoin, carbamazepine, and St. John's Wort) is prohibited. Avoid grapefruit and Seville oranges during ibrutinib treatment, as these contain moderate inhibitors of CYP3A.

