8.3 Excluded concomitant therapy

Use of the following therapies is prohibited during the study:

- Any therapies intended for the treatment of lymphoma/leukemia whether FDAapproved or experimental (outside of this study)
- Radiotherapy (Note: Localized radiotherapy to an area not compromising bone marrow function is allowed)
- Steroid therapy for anti-neoplastic intent. Short courses (<=14days) of steroid treatment for non-cancer related medical reasons (e.g. joint inflammation, asthma exacerbation, rash, antiemetic use and infusion reactions) at doses that do not exceed 100mg per day of prednisone or equivalent are permitted.
- Strong CYP3A inhibitors which would be taken chronically, with the exception of voriconazole and posaconazole, as outlined in section 8.2.1.
- Grapefruit, Seville oranges, Star fruit
- Strong CYP3A inducers (e.g. rifampin, rifabutin, phenytoin, carbamazepine, and St. John's Wort) are not recommended
- The use of warfarin is not allowed during this study

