15.0 STATISTICAL CONSIDERATIONS

- **15.1** This is a phase II single arm study of ibrutinib monotherapy in early stage CLL with a predicted time-to-treatment interval of less than 3 years, according to the MDACC nomogram developed by Wierda et al.(4) The primary objective is to evaluate the CR/CRi rate at two years. A maximum of 50 patients will be enrolled in the study with an estimated accrual rate of 4 patients per month; the accrual duration will be approximately 1 year.
- **15.2** The historical CR/CRi rate for patients who are treated when they have symptomatic disease requiring therapy, in the first line setting is 16% at 2 years (Pharmacyclics, internal data). We expect that early therapy with ibrutinib may increase this CR/CRi rate at two years from 16% to 30%. A sample size of 50 patients achieves 78% power to detect a difference of 14% in the 2-yr complete remission rate (i.e. to double the remission rate) using a one-sided binomial test. The target significance level is 0.05. These results assume that the population proportion under the null hypothesis is 16%.
- **15.3** For the primary analysis, we will calculate the proportion of patients with CR/CRi at 24 months, along with 95% confidence intervals. We will test the observed 2-year rate versus the null hypothesis of a 16% rate using a one-sided exact binomial test.
- 15.4 For secondary analyses, proportions of patients with objective response at 6, 12 and 24 months and CR/CRi at 6 and 12 months will be estimated along with 95% confidence intervals. The Kaplan-Meier method will be applied to estimate the progression free survival (PFS), the time to best response, the time to CR/CRi and time-to-alternative treatment survival curves. We will calculate the median time as well as the 2-year and 5-year survival rate and the corresponding 95% confidence intervals. In addition, we will directly compare the observed PFS time to each patient's individual predicted PFS time.

Protocol Amendments

Any amendments to the Protocol or Informed Consent Form must be sent to Pharmacyclics for review and approval prior to submission to the IRB. Written verification of IRB approval will be obtained before any amendment is implemented.

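### Section 6.0 prohibits chronic strong CYP3A inhibitors without exception, sections 8.2.1 and 8.3 allow voriconazole and posaconazole, and the voriconazole dose text is written for cGVHD rather than CLL

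*Combined protocol and SAP*

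**What the plan says.** The trial is a "phase II single arm study of ibrutinib monotherapy in early stage CLL" (section 15.1), and section 5.2 sets the regimen: "Ibrutinib monotherapy will be administered at 420mg once daily until either" one of the listed stopping points is reached.

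Strong CYP3A inhibitors are addressed in five places:

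- Section 4.2, exclusion 6: "Current and concurrent use of strong CYP3A4 inhibitors or activators". No drug is excepted.
- Section 6.0: "Concomitant use of strong CYP3A inhibitors which would be taken chronically" is prohibited, with examples and no exception.
- Section 7.5: strong CYP inhibitors are not permitted in subjects with chronic hepatic impairment. Again no exception is given.
- Section 8.2.1: strong inhibitors should be avoided, but "Voriconazole and posaconazole can be used concomitantly with ibrutinib". For the remaining strong inhibitors an alternative should be sought. If a strong inhibitor has to be used, dosing is to be discussed with the PI.
- Section 8.3, in the list of prohibited therapies: "Strong CYP3A inhibitors which would be taken chronically, with the exception of voriconazole and posaconazole, as outlined in section 8.2.1".

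On dosing, section 8.2.1 tells the physician, for moderate inhibitors, to "reduce the ibrutinib dose to 280 mg once daily for the duration of the inhibitor use". The passage for the two permitted strong inhibitors opens "In subjects with cGVHD, if a co-administration of voriconazole and posaconazole".

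**The concern.** A physician whose patient needs long-term voriconazole gets a different answer from section 6.0 than from section 8.3. One who follows 8.3 to 8.2.1 for the terms of the exception finds dose text addressed to a population outside this trial. The need is foreseeable: section 3.3 calls infection a leading cause of morbidity and mortality in CLL, and section 8.1 permits antifungal prophylaxis.

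The gap also runs against the protocol's own interaction data, since the weaker of the two interactions reported in B-cell malignancies has an explicit dose figure and the stronger has none. At stake are the safety of the patients concerned and uniform handling across a single-arm study.

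**Working it through.** The plan states no figure on this point to reproduce. The check is a comparison of texts plus one ratio, and it does not depend on sample size, power or significance level.

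**Step 1. Apply each section to the same patient.**

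| Situation on study | Section 6.0 | Section 8.2.1 | Section 8.3 |
|---|---|---|---|
| Voriconazole or posaconazole, chronic | Prohibited | Can be used | Excepted from the prohibition |
| Ritonavir, indinavir, nelfinavir, saquinavir or nefazodone, chronic | Prohibited | Should be avoided; PI discussion possible | Prohibited |
| Strong inducer | Prohibited | To be avoided | Called not recommended, inside the prohibited list |

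The first row is a direct contradiction. The second is a difference between a ban and a conditional allowance. The third is a difference in strictness only, because no section permits a named strong inducer.

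Section 7.5 adds a further case. A subject with chronic hepatic impairment may not take a strong inhibitor, but neither 8.2.1 nor 8.3 limits its exception for such subjects.

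**Step 2. Look for the dose text that the exception relies on.** Section 8.3 refers to 8.2.1. There the sentence covering voriconazole and lower-dose posaconazole is limited to cGVHD. The next sentence, on higher posaconazole doses, names no population. It sits between two cGVHD sentences, so its reach is uncertain. The sentence after it gives cGVHD subjects a different rule for moderate inhibitors, so the paragraph treats cGVHD as a separate group and its text cannot simply be read across to CLL. The paragraph also defers twice to the clinical study protocol. Since this is that protocol, those references lead nowhere.

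**Step 3. Compare the reported interactions.** Inputs, all from section 8.2.1 and both in B-cell malignancies:

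- voriconazole: Cmax 6.7-fold, AUC 5.7-fold
- erythromycin: Cmax 3.4-fold, AUC 3.0-fold

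Ratio = voriconazole fold-increase / erythromycin fold-increase.

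- AUC: 5.7 / 3.0 = 1.90
- Cmax: 6.7 / 3.4 = 1.97

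Section 8.2.1 also reports a maximal AUC increase of at most 2-fold in 37 subjects on mild or moderate inhibitors. That sits awkwardly beside the 3.0-fold figure, but it would widen the contrast (5.7 / 2 = 2.85), so the direction does not change.

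**The case against.** The strongest reply is that the gap is already covered. The PI sentence in 8.2.1 speaks of a strong inhibitor in general and could be read to include voriconazole and posaconazole. Section 8.2.1 asks for close monitoring, and section 7.0 lets the investigator adjust doses outside the guidelines. This stands in part. The PI sentence is ambiguous: it follows a sentence about all other strong inhibitors, so it may or may not reach the two permitted drugs. On either reading it gives no figure and does not resolve the conflict with section 6.0. So it would be too strong to say that CLL subjects have no instruction at all; what is missing is an explicit dose figure.

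Exclusion 6 is an entry criterion. Barring current users at enrolment is compatible with allowing a drug that becomes necessary later, so it adds tension rather than contradiction.

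A reader might infer several stronger things that the documents do not support:

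- **That sites would diverge.** No second treating site is documented; the outside center in section 5.3 concerns long-term follow-up. The inconsistency is between physicians.
- **That voriconazole is the largest documented interaction.** Ketoconazole is larger (AUC 24-fold in healthy subjects), and it has an instruction: avoid, or discuss with the PI. No exposure figure is given for posaconazole.
- **That all the voriconazole and posaconazole dose text is limited to cGVHD.** This is explicit for voriconazole and lower-dose posaconazole, and unclear for higher-dose posaconazole.
- **That the primary endpoint is biased.** A chain can be drawn from overexposure to toxicity, interruption (section 7), removal (section 13.0) and non-response through a missing assessment (section 11.0). However, no number of affected patients is given. Section 8.2.1 also reports no meaningful increase in toxicities among 66 subjects on moderate (47) or strong (19) inhibitors. Nineteen subjects give weak reassurance, but the chain remains unquantified.

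**Conclusion.** The concern holds as an internal inconsistency in the concomitant-medication text. Section 6.0 cannot be followed together with the exception in sections 8.2.1 and 8.3. Voriconazole, with an AUC increase 1.9 times that of erythromycin, has no explicit dose figure for this trial's patients, while moderate inhibitors do. The size comparison rests on voriconazole against erythromycin alone. The consequence is for patient safety and consistent conduct. The number of patients affected and any effect on the 24-month CR/CRi rate cannot be estimated from the documents. The differing strictness on inducers, and the absence of an exception in exclusion 6 and section 7.5, are secondary. The change should be made, but the statistical design does not depend on it.

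**What to change.** Reconcile sections 6.0, 8.2.1 and 8.3 so that one rule covers strong CYP3A inhibitors, with voriconazole and posaconazole named in it, and one rule covers strong inducers. Check exclusion 6 in section 4.2 and the hepatic-impairment bar in section 7.5 against the result, and state whether any exception applies there. Replace or remove the cGVHD text in 8.2.1, say whether the PI-discussion sentence covers the two named drugs, and drop the circular references to the clinical study protocol. Which rule and which dosing apply is for the sponsor to decide.

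The cost is a wording amendment through the usual review by Pharmacyclics and the IRB. Sample size, endpoints and analyses are unaffected.
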